05/18/2021

**Periapical Healing following Endodontic Microsurgery with
Collagen Based Bone Filling Material: A Randomized Controlled
Clinical Trial**

NCT04514991

Protocol:

Subjects are recruited for the study from the patient pool of the Department of Endodontics, School of Dental Medicine, University of Pennsylvania, who are planned for routine treatment of root end surgery. Patients who present to the post-doctoral resident clinic and meet the inclusion criteria are asked to participate in the study. The study includes lesions classes B and C, as described by Kim and Kratchman, J Endod 2006. Teeth designated as Class B present with a small periapical lesion, normal periodontal probing depth, and no mobility. Patients with such teeth often have clinical symptoms, and such cases are ideal for microsurgery. Teeth with Class C designation have a sizeable periapical lesion with a coronal extension of the lesion but without periodontal pocket or mobility.

Randomization is done for single-rooted teeth assigned as either control or test group receiving Foundation bone augmentation material (Morita, Tokyo, Japan). Osteotomy sites in the control group will be closed without placing bone filling material or membrane. For multirooted teeth with noncommunicating osteotomy sites, one osteotomy site is designated as control, and the other site is filled with Foundation bone filling material. Treatments for all patients in control and experimental groups follow the standard of care practices, routinely performed based on surgical guidelines as outlined in Kim and Kratchman, J Endod 2006.

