then curetted to induce bleeding inside of the surgical site. The co-investigator conducts the randomization of the case. Using a publicly available randomization application, Randomizer for Clinical Trials, single-rooted teeth will be assigned as either control or test group receiving Foundation. For multirooted teeth, the mesial root will be randomized, and the distal root will receive the other treatment. For teeth assigned to receive Foundation, a sterile instrument is used to remove the material from the plastic container and placed in the osteotomy site. In the control group, the osteotomy site is left unfilled, flap repositioned, and sutures placed. Patients are given post-operative instructions and scheduled for follow-up and suture removal 3-5 days after the surgery. PDM chart number, which is patient-specific are accessed only by the provider, PI and co-investigator (for follow-up procedures). Tooth number, gender, age, and list of potential clinical symptoms, the date of surgery (necessary only for a description of the study population for publication) are collected and forwarded to the principal investigator (PI). Several prognostic factors are evaluated such as subject's sex, age, tooth involved, diagnosis, clinical symptoms, lesion classification, treatment rendered before EMS (primary non-surgical root canal treatment, nonsurgical retreatment, previous history of apical surgery). Preoperative CBCT scan is evaluated for the following possible prognostic factors:

- 1) Presence of cortical plate fenestration. This information was verified clinically during surgery.
- 2) Thickness of the buccal bone: measured 3 mm coronally from the apex on the B-L view.
- 3) Lesion size: height, depth and width of the lesion were measured. The value of the largest dimension was recorded as the lesion size.
- 4) Root angulation: measured between the long axis of the root and a line tangent to the cortical plate at the resection area.

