Follow up visits are scheduled, as routinely practiced, every six months following the procedure. At six-month follow-up, periapical radiographs are taken. At 12-month follow-up, digital periapical radiographs and CBCT are obtained. In all follow-up visits, clinical signs and symptoms are evaluated. Molven's success criteria is applied to evaluate healing with periapical radiographs. For outcome assessment, cases will be designated as complete healing, incomplete healing, uncertain or unsatisfactory healing. Healing assessment on CBCT will be classified using modified PENN criteria as complete healing, limited, uncertain, or unsatisfactory healing. In complete healing, there is complete bone repair covering the resected root area, and the periodontal space is reformed with normal width or less than twice the width of the non-involved parts of the root. On the other hand, limited healing is characterized by complete healing in the vicinity of the resected root, but there is a discontinuity of the cortical plate with areas of low density. Low-density areas might also be present asymmetrically around the apex in limited healing or in the former access osteotomy. When the location of the low-density area is symmetrical around the apex or when the thickness is larger than twice the width of periodontal space, healing is classified as uncertain. Lastly, in unsatisfactory healing, the area of low density appears enlarged or unchanged. The co-investigator will be available during the follow-up appointments. All radiographs taken will be coded by case number (derived from the randomization table) and a suffix designating the time the radiograph was taken. Radiographs will be taken at three-time intervals PRE (preoperative, periapical, and CBCT), POP (immediate post-operative, periapical), FU1 (6-month follow-up, periapical), and FU2 (12-month follow-up,

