periapical and CBCT). Hence, every single radiograph can be traced accordingly by case number and interval. For example, 002-FU2 equals 12- month follow-up of case number 2. The co-investigator will not evaluate the radiographs herself, since she will be the only one able to reconnect case radiographs with the treatment used. Three calibrated endodontists (Examiner 1, 2, and 3) will evaluate the radiographs, blinded to the treatment used. Reviewers will assess the radiographs in a dark room using the same imaging software and taking standardized breaks. Preoperative and follow up CBCT will be assessed as described above using PENN 3D criteria. Cases with disagreement will be discussed until joint agreement is reached. Results will be recorded on an excel based score sheet and forwarded to the PI. After all radiographs are jointly agreed on by the examiners, without the interference of the PI, the PI will use the final score sheet(s) and rejoin the information obtained from the calibrated radiograph examination with the data from the material randomization table and information on possible clinical symptoms.

Statistical Analysis:

For subjects returning for 1 year follow up, the following statistical tests are completed:

- 1) Fisher's exact test to evaluate significant association between different healing categories and prognostic factors.
- 2) Logistic regression models were performed to assess odds of complete healing as a linear combination of prognostic factors.

The osteotomy site was considered as the unit of analysis. A probability of $P < .05$ was assigned as the level of significance.

Multiple imputation analysis was performed for cases lost to follow up using SAS statistical software to evaluate the association between the treatment arm and a particular outcome variable (2D healing, 3D healing, 2D outcome and 3D outcome). Under missing at random assumption (MAR), logistic regression analysis using all the variables from the completed cases was used to impute the missing data. Chi-square test for the independence between the outcome variable and treatment variable is carried out for each imputed data and results are pooled to generate a single p-value.

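### Split teeth place one site in each arm but sites are analysed as independent: tooth- and patient-level factor p-values may be too small and the treatment chi-square conservative

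*Combined protocol and SAP*

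**What the plan says.** Allocation mixes two designs. Single-rooted teeth are randomized in parallel, one site per tooth. In the randomization paragraph of the Protocol, multirooted teeth are split: "For multirooted teeth, the mesial root will be randomized, and the distal root will receive the other treatment". The opening of the Protocol describes the same split with a condition: "For multirooted teeth with noncommunicating osteotomy sites, one osteotomy site is designated as control". The later paragraph does not repeat that condition.

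The Statistical Analysis section then says "The osteotomy site was considered as the unit of analysis" and lists these methods:

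- Fisher's "exact test to evaluate significant association between different healing categories and prognostic factors".
- "Logistic regression models were performed to assess odds of complete healing as a linear combination of prognostic factors".
- After multiple imputation, a chi-square test of independence for "the association between the treatment arm and a particular outcome variable (2D healing, 3D healing, 2D outcome and 3D outcome"). The test is run on each imputed data set and pooled to one p-value.

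The factors include "sex, age, tooth involved, diagnosis, clinical symptoms, lesion classification, treatment rendered before EMS", plus four CBCT measures. Neither the Protocol nor the Statistical Analysis mentions pairing, clustering, a random effect, robust standard errors or a conditional analysis.

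**The concern.** A split tooth is a matched pair with one member in each arm. Its two sites share the patient and most of the listed factors, such as sex, age, tooth, diagnosis and earlier treatment. Positive correlation of healing within a tooth is therefore plausible, though the documents do not show it.

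If it exists, ignoring it has opposite effects on two kinds of comparison:

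- **Factors shared by both sites.** Two sites of one tooth count as two independent observations. The variance is understated and p-values are too small. Factor testing is what both numbered analyses in the plan describe, so spurious prognostic factors are the main risk.
- **Treatment.** The comparison is made within the split tooth, so the shared component cancels. An unpaired test overstates the variance, and p-values are too large. The possible cost is power.

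**Working it through.** **Inputs.** From the documents: the site as unit, one site per arm in split teeth, significance level 0.05, and the named tests. The documents give no sample size, healing rate, share of sites in split teeth (f) or within-tooth correlation (rho), and there is no figure of theirs to reproduce. Those values are assumed below, as are a two-sided test and 1:1 allocation.

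**Formula.** Take N sites, half in each arm, with outcome variance σ².

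1. Under independence, the difference between arms has variance 4σ²/N.
2. There are fN/2 split pairs. Each pair adds a covariance term of −2 × (2/N)² × rho × σ², because its members lie in opposite arms. The sum is −4·f·rho·σ²/N.
3. The ratio of true to assumed variance is therefore 1 − f·rho for treatment.
4. For a factor with the same value at both sites the sign reverses, giving 1 + f·rho. This takes the factor to be distributed alike in split and single-rooted teeth.
5. Actual type I error = 2 × [1 − Φ(1.96/√ratio)].

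| f | rho | f·rho | Treatment: 1.96/√ratio | Treatment error | Factor: 1.96/√ratio | Factor error |
|---|---|---|---|---|---|---|
| 0.2 | 0.1 | 0.02 | 1.980 | 4.8% | 1.941 | 5.2% |
| 0.25 | 0.2 | 0.05 | 2.011 | 4.4% | 1.913 | 5.6% |
| 0.5 | 0.4 | 0.20 | 2.191 | 2.8% | 1.789 | 7.4% |

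**Simulation under the null.** Assumed: 60 and 100 sites, 70% and 85% healing, and several category splits. Rejection rates at nominal 5%, with a rho = 0 baseline and then the same three cases:

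| Test | rho = 0 | 0.2, 0.1 | 0.25, 0.2 | 0.5, 0.4 |
|---|---|---|---|---|
| Tooth-level factor, logistic, 70% healing | 4.8–5.7% | 5.1–6.0% | 5.2–6.2% | 7.2–8.2% |
| Tooth-level factor, logistic, 85% healing | 3.0–5.3% | 3.4–5.6% | 3.5–5.3% | 4.4–7.1% |
| Tooth-level factor, two-category Fisher | 2.9–4.2% | 3.0–4.0% | 3.2–5.0% | 4.8–6.2% |
| Tooth-level factor, four-category Fisher | 3.7–5.2% | 4.4–5.6% | 4.9–6.2% | 7.9–9.2% |
| Treatment, two-category chi-square | 4.9–5.3% | 4.8–5.1% | 4.4–4.7% | 2.9–3.2% |

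The treatment deficit and the rise in factor error over baseline come from the correlation. In the logistic rows the covariates explain none of the correlation, so rho there is wholly residual. A root-level factor in the logistic model at 70% healing gave 4.8–5.3% at rho = 0 and 4.9–5.7% at rho > 0, so factors that vary independently between roots are little affected.

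**Power for treatment.** At an assumed 62% v 84% healed and 100 sites, the unpaired chi-square gave 71.5%, 72.4% and 73.6% in the three cases. A permutation test that follows the randomization gave 71.0%, 72.2% and 79.5%. Only the last case shows a gain.

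**The case against.** The strongest reply is about weight. Without f and rho, nothing shows that the effect is material. At f = 0.25 and rho = 0.2 the logistic rates of 5.2–6.2% overlap their own baseline of 4.8–5.7%. With 4,000 runs per cell, Monte Carlo error alone is about 1.96 × √(0.05 × 0.95/4,000) = 0.7 points. Two-category Fisher stays at or below 5.0% in both milder cases. The shared factors cited as the source of correlation are themselves candidates for the logistic model, so only residual correlation matters there. The plan names no confirmatory factor hypothesis.

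All of this stands, and it limits the size. It does not remove the mismatch between allocation and analysis. Fisher's offset applies to two categories. The plan speaks of different healing categories, and the outcome-assessment paragraph of the Protocol defines four: "Healing assessment on CBCT will be classified using modified PENN criteria as complete healing, limited, uncertain, or unsatisfactory healing". The plan also lists 2D and 3D healing separately from 2D and 3D outcome, without saying which variables have four levels.

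A reader might infer that ignoring the pairing inflates the Foundation-versus-control comparison. The documents do not support this: split sites lie in opposite arms, so positive correlation makes that test conservative. A reader might also infer that every prognostic p-value is too small. CBCT measures can differ between roots, and their error depends on how alike they are within a tooth.

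**Conclusion.** The point holds as a mismatch between the stated randomization and the stated analysis, and it should be fixed. The directions are firm if healing correlates positively within a tooth: factor p-values at tooth and patient level too small, treatment chi-square conservative. The size is not firm. It runs from negligible (4.8% for treatment and 5.2% for a factor) to clear (2.8% and 7.4%) over the assumed range. The documents do not show that the trial lies at the upper end. They do not give the share of split teeth, and the two descriptions of which multirooted teeth are split differ and must be reconciled. Confidence is medium for that reason.

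**What to change.** Change the Statistical Analysis section as follows.

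1. **Binary outcomes, including complete healing.** Fit the factor and treatment models as logistic GEE clustered on tooth (on patient, if a patient can give more than one tooth), with a small-sample-corrected variance and root type as a term.
2. **Category-by-factor tests.** Permute tooth-level factors by whole tooth within root type, and patient-level factors by patient if a patient can give more than one tooth. Test factors that fix root type, such as tooth involved, in the clustered model only.
3. **Imputation.** Keep both sites of a tooth linked. For binary outcomes, pool the clustered treatment log odds ratio by Rubin's rules in place of the unpaired chi-square. For four-category outcomes, pool either a clustered proportional-odds log odds ratio or a clustered multi-parameter Wald test, chosen in advance.
4. **Fallback.** Where the clustered model does not converge, report a complete-case permutation test that swaps arms within split teeth and permutes arms among single-rooted teeth.
5. **Reporting.** Give the number of split teeth and the estimated within-tooth correlation.

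In the same simulations at rho > 0 and 70% healing, the GEE (independence working correlation, Kauermann-Carroll variance) gave 4.1–4.8% for treatment and 4.0–5.4% for tooth-level factors. The treatment permutation test (two categories, mid-p) gave 4.3–5.0% in every cell. Whole-tooth permutation of a factor gave 3.8–5.4% on four categories and 2.8–4.4% on two.

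The fallback is needed. At 85% healing and 60 sites the GEE failed in 7.5–19.7% of runs, and ordinary logistic regression failed in the same runs. Linked imputation and the pooled four-category analyses were not simulated.

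The cost is modest programming and less favourable factor p-values. There is no treatment gain if few teeth are split or the correlation is weak. No new patients or data are needed.

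### The treatment test is one unstratified, unpaired chi-square over all osteotomy sites, although single-rooted teeth form a parallel comparison and multirooted teeth a within-tooth comparison

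*Combined protocol and SAP*

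**What the plan says.** The Protocol describes two assignment schemes. In the first, "single-rooted teeth will be assigned as either control or test group receiving Foundation". In the second, "For multirooted teeth, the mesial root will be randomized, and the distal root will receive the other treatment". For multirooted teeth whose sites do not communicate, the opening section says the same in other words: "one osteotomy site is designated as control, and the other site is filled with Foundation bone filling material". So each such tooth puts exactly one site in each arm.

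Statistical Analysis then treats all sites alike: "The osteotomy site was considered as the unit of analysis". Treatment is tested only after multiple imputation: "Chi-square test for the independence between the outcome variable and treatment variable is carried out for each imputed data", and the results are pooled to one p-value. The significance level is fixed by "A probability of $P < .05$ was assigned as the level of significance". No stratum, pairing or clustering term is named.

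The other analyses do not fill the gap. The regression is described as "Logistic regression models were performed to assess odds of complete healing as a linear combination of prognostic factors", and treatment arm is not named as a term. The factor list begins "Several prognostic factors are evaluated such as subject's sex, age, tooth involved, diagnosis, clinical symptoms, lesion classification". Tooth is on it; mesial or distal position is not named. The imputation model may contain tooth, but that does not stratify the test that follows.

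**The concern.** The analysis does not follow the design. A chi-square test of independence on all sites treats the two sites of one tooth as unrelated, and it mixes a between-tooth comparison with a within-tooth one. Three things are at stake.

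- **Calibration and power.** If two sites in one mouth and one tooth heal alike, the within-tooth difference is less variable than the test assumes. The p-value is then too large on average and power is lost.
- **Chance imbalance.** If the single-rooted teeth split unequally, multirooted sites make up a different share of each arm. If the mesial draws split unequally, root position differs between arms. Both can be known for every site, yet neither is adjusted for.
- **Interpretation.** The reader gets one p-value and cannot see whether the two comparisons agree.

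**Working it through.** The plan states no sample size, healing rate, effect size, allocation ratio or within-tooth correlation, so there is no figure to reproduce. Every input below is an assumption unless it is cited from the plan.

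**1. Systematic bias.** Each multirooted tooth adds one site to each arm and its mesial arm is drawn at random. Under 1:1 allocation, tooth type and root position are therefore balanced in expectation. In simulation under the null (40,000 runs per setting), the mean pooled risk difference was at most 0.0013 in absolute value, even with gaps of 20 to 40 points by tooth type or root position. If single-rooted teeth were allocated 2:1 and prognosis differed by tooth type, the mean shift would be 3.0 to 5.3 points. The plan does not state the ratio.

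**2. Chance imbalance in tooth type.** Assume 40 single-rooted and 20 split teeth with simple 1:1 randomisation.
- The 95% range of Binomial(40, 0.5) is 14 to 26. A split of 14:26 or worse has probability 8%.
- At 14:26 the multirooted share is 20/34 = 58.8% in one arm and 20/46 = 43.5% in the other.
- With a 15-point prognosis gap, the shift is 15 × (0.588 − 0.435) = 2.3 points.
- Variant with 10 split teeth and healing of 85% single, 65% split: (26×0.85 + 10×0.65)/36 − (14×0.85 + 10×0.65)/24 = 0.794 − 0.767 = 2.8 points. At 90%/60% it is 4.2 points.

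**3. Chance imbalance in root position.** With K split teeth, k of them drawn Foundation-mesial, and a mesial-distal gap δ, the split-tooth difference shifts by δ(2k/K − 1). This has mean zero and SD δ/√K.
- For K = 20 and δ = 15 points, the SD is 15/√20 = 3.4 points.
- A 13:7 or worse draw has probability 0.263. At 13:7 the shift is 15 × (26/20 − 1) = 4.5 points.
- That applies to split teeth only. With about 20 of 40 sites per arm from split teeth, the pooled shift is 4.5 × 20/40 ≈ 2.3 points and the SD about 1.7.

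**4. Calibration and power.** Simulations used a shared latent tooth effect with correlation 0, 0.3 or 0.6 and mixed single/split counts of 40/10, 30/15, 20/20 and 60/30. The comparison is the pooled Pearson chi-square against a Cochran-Mantel-Haenszel (CMH) test with single-rooted teeth as one stratum and each split tooth as its own. There were no missing data; imputation was not simulated.

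| Setting | Pooled | CMH |
|---|---|---|
| Type I, mixed, correlation 0.6, mesial-distal gap up to 20 points | 0.019–0.038 | 0.046–0.051 |
| Type I, mixed, correlation 0, gap 40 points | 0.054–0.062 | 0.046–0.051 |
| Power, 30/15, control healing 75%/45%, correlation 0.3 | 0.39 | 0.48 |
| Power, 60/30, control healing 75%/45%, correlation 0.6 | 0.70 | 0.85 |
| Power, 30/15, no tooth-type gap, correlation 0 | 0.44 | 0.42 |

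The CMH range is over all mixed settings; power is for a 20-point effect. With split teeth only (30), type I error ran from 0.011 to 0.070 pooled and from 0.042 to 0.052 with CMH.

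**5. Where the gain comes from.** Tooth-type strata alone add nothing at a 15-point prognosis gap (40/20 teeth, independent sites: type I 0.051 pooled against 0.050 stratified; power 0.526 against 0.528). At a 30-point gap they add 3 to 5 points of power. Making each split tooth a stratum as well brings type I error from about 0.027 back to 0.05 at correlation 0.6, and adds roughly 8 to 17 points of power over the pooled test.

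**6. Combining the two parts.** Inverse-variance weighting of the two component estimates gave type I error of 0.06 to 0.08, so it is not a safe substitute at these counts.

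**The case against.** A reader might infer that tooth type and root position bias the arm comparison. The documents do not support that: the complementary assignment and the random mesial draw balance both in expectation, and an unadjusted test of a randomised comparison already allows for chance imbalance. Bias on average would need unequal allocation of single-rooted teeth, which the plan neither states nor excludes.

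The imbalance is also small. With 80 sites the standard error of the pooled difference is about 10 points, so a 2.3-point tail shift is about 0.2 standard errors. Stratifying by tooth type alone changes almost nothing unless the prognosis gap is large. That stands, and it is why pairing has to be part of the remedy.

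A reader might also infer that root position cannot be handled at all because it is not on the factor list. The list is introduced as examples, and arm is assigned by root, so position should be recoverable. Nor would adjusting for it buy much. In paired simulations the standard error went from 0.139 to 0.139 at K = 20 with a 15-point gap. At K = 40 it went from 0.098 to 0.097 (about 1%) with a 15-point gap and from 0.100 to 0.095 (5%) with a 20-point gap.

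What the objection does not remove is the mismatch itself: no stated analysis of treatment uses the pairing or the tooth-type strata.

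**Conclusion.** The point holds as a mismatch between design and analysis, not as a source of bias under 1:1 allocation. Unadjusted chance imbalance is worth about 2 to 3 points on the pooled difference in tail cases, for prognosis gaps of 15 to 20 points. The larger effect is on the test: with positive within-tooth correlation it is usually conservative and less powerful than one that follows the design. It exceeds the nominal level only in less likely settings, such as a 40-point mesial-distal gap with no correlation, or unequal allocation combined with a tooth-type gap. All sizes depend on assumed counts, rates and correlations, and imputation was left out of the check. This is a worthwhile, low-cost improvement rather than a defect that undermines the trial.

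**What to change.** - In each imputed data set, replace the pooled chi-square with a Mantel-Haenszel test and estimate that takes single-rooted teeth as one stratum and each multirooted tooth as its own. An equivalent conditional or clustered logistic model with a tooth-type term would also serve. Pool across imputations.
- For any outcome kept in its four healing categories, use the extended CMH test with the same strata.
- Show the single-rooted and split-tooth estimates side by side, with confidence intervals. Do not combine them by inverse variance at small counts.
- Record mesial or distal for each site, and adjust for root position as a sensitivity analysis only.
- State the allocation ratio for single-rooted teeth, since the absence of systematic bias rests on it.

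The cost is SAP wording and one data column; clinical care is not affected. The component estimates are less precise than the pooled one, and there is little or no gain (0.42 against 0.44 power in the example above) if within-tooth correlation is zero and prognosis does not differ by tooth type.

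### Foundation versus control is written only as a site-level chi-square pooled to a p-value: no effect estimate or interval is stated, and opposite-arm pairs within a tooth are ignored

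*Combined protocol and SAP*

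**What the plan says.** Allocation has two forms. In the Protocol section, "Randomization is done for single-rooted teeth assigned as either control or test group", so each of these teeth supplies one site. "For multirooted teeth with noncommunicating osteotomy sites, one osteotomy site is designated as control", and the other site is filled with Foundation. The later randomization paragraph confirms this: "For multirooted teeth, the mesial root will be randomized, and the distal root will receive the other treatment".

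The Statistical Analysis section gives two analyses for subjects who return at one year. Item 1 is Fisher's exact test "to evaluate significant association between different healing categories and prognostic factors". Item 2 reads: "Logistic regression models were performed to assess odds of complete healing as a linear combination of prognostic factors". Neither names the arm. The Protocol introduces the factors with "Several prognostic factors are evaluated such as". The list is therefore open, but the only treatment it mentions is treatment given before the surgery.

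The section then states: "The osteotomy site was considered as the unit of analysis". It names no paired or clustered method.

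The arm appears only in the closing imputation paragraph, against four outcome variables (2D and 3D healing, 2D and 3D outcome). There a chi-square test of outcome against treatment "is carried out for each imputed data and results are pooled to generate a single p-value". This is best read as one p-value per outcome.

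**The concern.** There are two gaps in the comparison that the trial was randomized to make.

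First, a pooled p-value does not show how large a benefit the data support or rule out. The documents give no sample size or target difference, so a reader could not tell whether a non-significant result excludes a useful effect.

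Second, the chi-square assumes independent sites, while each two-site tooth supplies a matched pair across the arms. The standard error of the arm difference is then wrong whenever healing is correlated within a tooth. An ordinary logistic model under item 2 shares the fault. For the factors in items 1 and 2 that both sites of a tooth have in common, the error has the opposite sign.

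**Working it through.** The plan states no sample size, power, healing rate or effect size, so there is no design figure to reproduce.

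**Inputs from the documents.** Significance level 0.05; unit of analysis the site; the two sites of a multirooted tooth in opposite arms.

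**Inputs assumed.** f, the share of sites that lie in two-site teeth; rho, the within-tooth correlation of healing; n sites per arm, with equal arms and healing probability p in both.

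**Arm comparison.** There are f·n pairs, and each contributes a covariance rho·p(1−p) between the arms:

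- Var(difference) = [2p(1−p)/n] × (1 − f·rho)
- The chi-square uses 2p(1−p)/n
- True size = 2Φ(−1.96/√(1 − f·rho))
- An interval built on the same site-level variance is too wide by the factor 1/√(1 − f·rho)

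| f | rho | 1 − f·rho | True size | Interval too wide by |
|---|---|---|---|---|
| 0 | any | 1.00 | 5.0% | 0% |
| 0.2 | 0.3 | 0.94 | 4.3% | 3% |
| 0.3 | 0.3 | 0.91 | 4.0% | 5% |
| 0.6 | 0.3 | 0.82 | 3.0% | 10% |
| 0.6 | 0.5 | 0.70 | 1.9% | 20% |

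The sign of rho matters. At rho = −0.2 the size is 6.2% with half the sites in pairs (1 − f·rho = 1.1) and 7.4% with all of them (1.2).

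**Factors shared by both sites of a tooth.** The two sites now fall in the same factor group, so the multiplier becomes 1 + f·rho. A large-sample site-level test has size 2Φ(−1.96/√1.06) = 5.7% at f = 0.2, rho = 0.3, and 2Φ(−1.96/√1.30) = 8.6% at f = 0.6, rho = 0.5. Fisher's exact test is itself conservative in small tables, so item 1 may absorb part or all of this. A Wald test in item 2 has no such cushion.

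**Why a p-value is not enough.** Uncorrected Pearson chi-square, Newcombe intervals, independent sites:

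- 45/50 versus 40/50: p = 0.161, difference 10 points, 95% CI −4 to 24
- 22/25 versus 18/25: p = 0.157, difference 16 points, 95% CI −7 to 37

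The p-values are almost the same, but the upper limits differ by 13 points.

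**Simulation of the remedy.** Settings: 40, 60 and 100 sites, f from 0 to 0.6, rho up to 0.5, 80% healed in both arms. The remedy is the risk difference with tooth-clustered variance × G/(G−2) and t on G−2 degrees of freedom, where G is the number of teeth.

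- No loss: size 2.0–5.1% for the chi-square and 4.2–5.4% for the clustered difference. The clustered CI covers 94.5–95.8%.
- Without the small-sample correction and with a normal reference, the clustered size at 40 sites is 5.7–6.9%.
- With 20% of teeth lost, complete-case clustered size is 3.6–5.8%.
- With the same loss and site-by-site imputation, size is 1.7–5.1% for the pooled chi-square and 2.0–5.0% for the pooled clustered difference.
- Power at 90% versus 70% healed, clustered minus chi-square: −1 to +14 points with no loss, and −2 to +7 points with 20% loss and imputation.

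**The case against.** The strongest reply is that the text is brief and the arm may well belong in item 2. The factor list is open, item 2 models odds, and the Protocol says that the examiners' scores are rejoined with the randomization table just before analysis. On that reading an odds ratio for the arm was intended. This stands as a possibility, and so the point is only that the arm effect and its interval are not written. A reader might infer that the trial planned no estimate at all, or no complete-case comparison of the arms. The documents do not support that.

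A second reply is that the pairing problem rests on assumed inputs. This is also right. At f = 0.2 and rho = 0.3 the loss is minor, and with no pairs it vanishes. Two stronger readings are tempting. One is that ignoring clustering inflates false positives for the arm. Under positive correlation it does the reverse, because the paired sites sit in opposite arms. The other is that the arm test is conservative whatever the data. That needs positive correlation, which is natural for two roots of one tooth but is not given.

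Third, clustering brings little to the imputed analysis if imputation ignores the tooth, as the simulated sizes show. This stands, and it is why the complete-case result has to be shown beside it.

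Finally, much of the section is in the past tense, so some choices may no longer be possible in advance. The estimate, its interval and the clustered variance can still be produced from the same data.

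**Conclusion.** The point holds as a cheap improvement. Two things are secure from the text. The arm is named in the Statistical Analysis section only through a pooled site-level chi-square, with no effect estimate or interval written. And two-site teeth place one site in each arm while the analysis treats sites as independent.

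The size of the calibration error is conditional. Under positive within-tooth correlation the arm test is conservative, with true size between 4.3% and 1.9% across the assumed cases. It is correct with no pairs or no correlation, and mildly anti-conservative if the correlation is negative. For factors shared within a tooth, positive correlation raises the error rate. The need for an estimate and interval depends on none of these assumptions. The simulations treat healing as a yes/no outcome, which the plan does for item 2 but does not state for all four outcome variables.

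**What to change.** - State Foundation versus control as the main analysis, for complete healing at 12 months. Both the CBCT reading (modified PENN criteria) and the periapical radiograph reading have a complete-healing category, so name in advance which is the main one and report the other as secondary.
- Report the unadjusted risk difference, and the odds ratio, with 95% CI and p-value. Use tooth-clustered variance × G/(G−2) and t on G−2 degrees of freedom. The correction must be named, because the calibration depends on it.
- Show complete cases first. Then show the imputed data, with the arm stated in the imputation model and estimates combined by Rubin's rules.
- Include the arm as a term in the item 2 models, and use tooth-level clustering for all their terms.
- Keep covariate adjustment optional: few covariates, fixed before the arm is rejoined to the scores, and only with enough non-healed sites. In simulation an adjusted logistic model failed or separated in 6–25% of data sets at 40 sites. The unadjusted clustered difference failed in at most 0.1%.
- If an arm has no non-healed site, give a Newcombe interval that ignores pairing, and say that it does.

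The cost is SAP wording and slightly more analysis, using standard SAS procedures on data already collected. With no pairs the only gain is the estimate and its interval. With few pairs or weak correlation the calibration and power gain is small, and it is also small in the imputed analysis if imputation ignores the tooth.
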